#### **4. ANALYSIS POPULATIONS**

In this study, three analysis populations are defined: Safety Population, Pharmacokinetic Population, and Pharmacodynamic population. Data for Screen Failures will not be included in any summary tables, figures, or data listings. Subjects included in the defined (various) analysis populations will be decided at the blinded data review meeting prior to unblinding of NHV cohorts. The same process will be applied to the CHB cohorts as well even if there is no blinding for these cohorts.

Furthermore, any additional analysis populations not identified in the SAP will be identified in the final CSR as post hoc analyses. This may include the addition of additional study populations or subgroups of interest.

The number and percentage of subjects in each analysis population will be summarized.

##### *Safety Population*

All subjects who receive at least one dose of study treatment (ARO-HBV or JNJ-6379) will be included in the Safety Population. Subjects will be summarized according to the treatment they received.

All safety, treatment exposure, demographic and baseline characteristic data will be listed and summarized using the Safety Population.

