Safety population: All participants (NHV and CHB patients) that received at least one dose of ARO-HBV or JNJ-6379.

Unless otherwise specified, for data analysis purposes baseline will be defined as pre-dose on Day 1.

Immunology Assessments (limited number of CHB patients in New Zealand only)

Immunology parameters will be summarized by cohort for the following:

- Changes in profile from pre-dose to post-dose time points for: T cell subsets (activation and exhaustion state), NK cell subsets (activation and exhaustion state), B cell subset, monocyte subsets. To be conducted if scientifically feasible.
- Changes from pre-dose to post-dose time points for: HBV antigen specific T cell response (including

HBcAg, HBsAg). To be conducted if scientifically feasible.

Virology assessments (CHB patients only)

Virologic parameters will be summarized by cohort for the following:

- Quantitative HBsAg (qHBsAg: Log change from baseline to nadir and duration of response from nadir back to approximately 20% of baseline or EOS
- Percent of patients with loss of HBsAg (defined as HBsAg < 0.05 IU/mL) at EOS and time to occurrence (Kaplan Meier)
- Percent of patients with anti-HBs seroconversion at EOS and time to occurrence (Kaplan Meier).
- Change in Anti-HBs (quantitative) over time
- Quantitative HBV DNA (when quantifiable at baseline): Log change from baseline to EOS
- Quantitative HBV RNA: Log change from baseline to nadir and duration of response from baseline to EOS (if scientifically feasible)
- Quantitative HBcrAg: Log change from baseline to nadir and duration of response from baseline to EOS
- Quantitative HBeAg (where applicable): Log change from baseline to nadir and duration of response from baseline to EOS
- Emergence of HBV mutations (sequencing of ARO-HBV target site, Core/pre-core, HBsAg epitope, any other mutations by deep sequencing)

Descriptive statistics of virologic parameters will include mean, median, count, SD, minimum, and maximum. Additional details will be provided in the statistical analysis plan.

Separate analysis will be completed for all CHB patients receiving at least one dose, all HBeAg negative patients and all HBeAg positive patients, all treatment naïve and all entecavir or tenofovir experienced patients.

Pharmacokinetics (NHV subjects and limited PK in Cohort 12):

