## **2.4 Sample Size**

No formal statistical calculation of sample size will be used for this Phase 1/2a study. The sample size is empirical. The small numbers per cohort in this study are not intended for statistical hypothesis inference analysis. Results from this study will be utilized in sample size calculations for subsequent studies.

This study will involve approximately 30 eligible normal healthy volunteers in NHV cohorts and a minimum of 60 and a maximum of 84 CHB patients in CHB cohorts. Each of the 5 NHV cohorts will recruit 6 healthy volunteers. CHB cohorts 1b, 1c, 2b, 3b, 4b and 5b will recruit a minimum of 4 and a maximum of 8 patients, and CHB cohorts 6, 7, 8, 9, 10, 11 will recruit a maximum of 4 CHB patients. Cohort 12 will recruit 12 CHB patients.

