## **2.5 Randomisation**

### NHV Cohorts

The six (6) healthy volunteers in each of the five (5) NHV cohorts will be randomized at a ratio of 2:1 (active: placebo) to receive ARO-HBV or Placebo in a double-blind fashion. Therefore 4 subjects will be randomized to receive ARO-HBV and 2 subjects to receive placebo in each of the NHV cohorts.

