##### *Pharmacodynamic (PD) Population*

Subjects who received at least one dose of study treatment (ARO-HBV, JNJ-6379, or placebo) and had PD assessment from baseline and  $\geq 1$  assessment from post-baseline will be included in the PD population. Subjects will be summarized according to the treatment they received.

Subjects with protocol violations will be assessed on a subject-by-subject basis for inclusion in the PD Population. The determination of study populations will be made, prior to unblinding the PD data, at the blinded data review meeting before the final analyses. The PD population will be used for the summaries of all immunologic endpoints, virology endpoints, cytokines and complement.

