### **10.1 Adverse Events**

Adverse events (AEs) will be coded using the Medical Dictionary for Regulatory Activities (MedDRA®, the latest available version), and data will be summarized by System Organ Class (SOC) and Preferred Term (PT). The number and percent of subjects reporting each AE will be summarized for each dose level (cohort) and overall. A subject with two or more AEs within the same level of summarization (i.e., SOC or PT) will be counted only once in that level. Percentages will be based on the number of subjects in the Safety Population within each dose level (cohort). The number of AEs reported will also be presented.

Treatment-emergent AEs (TEAEs) are defined as pre-treatment existing conditions that worsen after study drug administration, or events that occur during the course of the study during or after administration of study drug. Only TEAEs will be included in the AE summary tables which will present data by dose level (NHV/CHB cohorts) for active treatment versus pooled placebo subjects (NHV cohorts). In the case of a missing AE start date or stop date, the most conservative approach will be followed to classify AE into TEAE unless it is not possible that the AE could be treatment emergent. AEs that occurred during the follow-up period will only be included in the follow-up table.

A table providing an overall summary of AEs will be produced which will include the number of TEAEs; the number and % of subjects reporting at least one: TEAE, serious TEAE, grade 3 (severe) or higher TEAE, TEAE related to study treatment (related to ARO-HBV or JNJ-6379 [Cohort 12 only]: possibly/probably), serious TEAE related to study treatment, grade 3 or higher TEAE related to the study drug, TEAEs by severity and TEAEs by relationship, drug or study discontinuations due to TEAEs. The table will also be repeated for related (ARO-HBV or placebo) TEAEs.

Additional AE tables will be generated as follows:

- TEAEs by SOC and PT
- TEAEs by decreasing incidence of the PTs in the Combined ARO-HBV group
- Study Drug (ARO-HBV or placebo) Related TEAEs by SOC and PT
- Study Drug (ARO-HBV or placebo) Related TEAEs by decreasing incidence of the PTs in the Combined ARO-HBV group
- Study Drug (JNJ-6379) Related TEAEs by SOC and PT (Cohort 12 only)

- Study Drug (JNJ-6379) Related TEAEs by decreasing incidence of the PTs in the Combined ARO-HBV group (Cohort 12 only)
- TEAEs by Severity
- TEAEs by Relationship to Study Drug (ARO-HBV)
- Treatment Emergent SAEs

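### The Safety Population is limited to subjects dosed with ARO-HBV or JNJ-6379, so all 10 planned placebo volunteers fall outside it and the pooled-placebo safety comparator is empty as written

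*SAP*

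**What the plan says.** The SAP (Section 4, Safety Population) defines entry by drug received: "All subjects who receive at least one dose of study treatment (ARO-HBV or JNJ-6379) will be included in the Safety Population". The protocol synopsis, under Data Analysis, agrees: "Safety population: All participants (NHV and CHB patients) that received at least one dose of ARO-HBV or JNJ-6379". The SAP adds that subjects are summarised by the treatment they received, and it assigns all safety, exposure, demographic and baseline data to this population. SAP Section 5 puts disposition on it, and Section 10 puts every safety endpoint on it.

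For adverse events, SAP Section 10.1 says the summary tables will "present data by dose level (NHV/CHB cohorts) for active treatment versus pooled placebo subjects (NHV cohorts", and sets the denominator: "Percentages will be based on the number of subjects in the Safety Population within each dose level (cohort".

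The other two populations in SAP Section 4 deal with placebo expressly. The PD Population takes "Subjects who received at least one dose of study treatment (ARO-HBV, JNJ-6379, or placebo", subject to having baseline and post-baseline data. The PK Population rules out subjects who received placebo only.

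**The concern.** A volunteer randomised to placebo receives 0.9% saline and nothing else. Read as written, the Safety Population rule excludes every such volunteer, and with them the comparator that the adverse event tables are built around.

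The primary objective is the incidence and frequency of related adverse events, as a measure of safety and tolerability. Protocol Section 6.2 gives reduced bias in that assessment as the reason for including placebo. All chronic hepatitis B patients are on open-label active treatment, so the blinded placebo volunteers are the only concurrent control in the study. Without them, nothing in the tables separates drug effects from events caused by confinement, repeated blood sampling or the injection itself.

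There is also a procedural difficulty. SAP Section 4 has population membership settled at a blinded review before the healthy-volunteer cohorts are unblinded. Under the written rule, whether a volunteer belongs to the Safety Population depends on the arm, which is not known at that meeting.

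**Working it through.** **Inputs**
- Healthy-volunteer cohorts (SAP 2.4): "Each of the 5 NHV cohorts will recruit 6 healthy volunteers".
- Stated total (SAP 2.4): "This study will involve approximately 30 eligible normal healthy volunteers in NHV cohorts".
- Allocation (SAP 2.5): "Therefore 4 subjects will be randomized to receive ARO-HBV and 2 subjects to receive placebo in each of the NHV cohorts".
- Healthy volunteers receive a single dose, with no later active dose (Protocol 6.1).
- JNJ-6379 goes to Cohort 12 only (Protocol 8.8).
- All chronic hepatitis B patients receive active treatment (Protocol 9.4).
- Chronic hepatitis B enrolment is 60 to 84 (SAP 2.4).

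**Reproducing the plan's totals**
- Healthy volunteers: 5 × 6 = 30, as stated. Active: 5 × 4 = 20. Placebo: 5 × 2 = 10.
- Chronic hepatitis B patients: six cohorts of 4 to 8, six cohorts of 4, and Cohort 12 with 12. Minimum 6 × 4 + 6 × 4 + 12 = 60; maximum 6 × 8 + 6 × 4 + 12 = 84. Both match.

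**Applying the rule**

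| | As written | Placebo named |
|---|---|---|
| Active volunteers | 20 | 20 |
| Placebo volunteers | 0 | 10 |
| Healthy-volunteer Safety Population | 20 | 30 |
| Whole-study Safety Population | 20 + 60 = 80 to 20 + 84 = 104 | 30 + 60 = 90 to 30 + 84 = 114 |

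The excluded share is 10/30 = 33% of healthy volunteers and 10/10 = 100% of the control group.

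**What the control would show.** As an illustration, assume a background adverse event rate p in volunteers. The chance of at least one such event among 10 placebo subjects is 1 − (1 − p)^10:
- p = 0.10: 0.651
- p = 0.20: 0.893
- p = 0.30: 0.972

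The group is small, but it would usually reveal a common background event. With n = 0 it reveals nothing.

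**Setting the definition against the planned outputs**
- SAP Section 3 specifies healthy-volunteer columns for combined placebo and for a total that includes placebo.
- SAP Section 8 presents study drug administration on the Safety Population and counts placebo among the study drugs.
- SAP Section 10.1 plans tables of events related to ARO-HBV or placebo.
- SAP Section 20 assigns the healthy-volunteer randomisation listing to the Safety Population.

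None of these can be produced in full from a population that contains no placebo subjects.

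**The case against.** The strongest reply is that the intent is plain. The placebo columns, the exposure section, the related-event tables and the randomisation listing all presuppose placebo subjects in the safety outputs. The protocol synopsis counts placebo among the study treatments, and study treatment is the main term in the SAP definition. The PK Population has an explicit placebo exclusion; the Safety Population has none. The amendment summary for Version 5.0 suggests how the wording arose: when the JNJ-6379 cohort was added, the general term was replaced by the two drug names, and the stated rationale says nothing about removing placebo volunteers. Protocol Section 11.4 summarises safety by cohort and treatment group without any such limit. An analyst would probably raise a query before delivering an empty column. The objective itself names no placebo comparison, and the safety methods are descriptive.

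Most of this stands as evidence of intent, and it shows that the exclusion is a slip. It does not repair the definition. Study treatment alone would have covered placebo; the parenthesis that follows narrows it to two drugs. A reader who compares the three population definitions side by side sees placebo addressed in two and absent from the third. Summarising by treatment received decides which column a subject appears in, not whether the subject enters the population. If the analyst includes placebo anyway, the analysis departs from its stated population, and SAP Section 4 treats populations not identified in the SAP as post hoc.

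**Conclusion.** The concern holds. As written, none of the 10 planned placebo volunteers meets the Safety Population rule, the pooled-placebo denominator is 0, and the planned comparison of active with placebo cannot be made. The definition contradicts the outputs it governs.

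The effect is confined to the healthy-volunteer part. Counts within each active cohort do not change, the chronic hepatitis B tables are unaffected, and no placebo data go uncollected. With no hypothesis test, neither alpha nor power is involved. The count of 10 assumes full enrolment at the planned 4:2 allocation, without replacements. The consequence rests on applying the definition literally, but a governing population definition should give the right answer when applied literally, particularly where it supports the primary objective.

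**What to change.** In SAP Section 4, define the Safety Population as all subjects who receive at least one dose of ARO-HBV, JNJ-6379 or placebo, using the same three-item list as the PD Population. Keep the existing sentence on summarising by treatment received. Make the matching change in the protocol synopsis. Every dosed volunteer then qualifies whatever the arm, so Safety Population membership can be settled at the blinded review.

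The cost is one phrase in each document. No new data, tables or analyses are required.

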##### *Pharmacokinetic (PK) Population*

Subjects who have received the active treatment (ARO-HBV) and have adequate PK data to characterize PK profile will be included in the PK Population. This includes NHV Cohorts 1, 2, 3, 4 and 5 and CHB Cohort 12 subjects that received at least one dose of active study treatment (ARO-HBV).

Subjects who prematurely discontinue from the study will be included in the Safety Population but may not be included in the PK Population if they do not have PK data to contribute to the analyses. Subjects with missing sample concentrations will be included in the PK analyses provided their PK parameters can be adequately characterized based upon the remaining data. Subjects who received only placebo will be excluded from the PK population. The PK population will be used for the summaries of all PK data.

Subjects with protocol violations will be assessed on a subject-by-subject basis for inclusion in the PK Population. The determination of study populations will be made, prior to unblinding the PK data, at the blinded data review meeting before the final analyses for NHV Cohorts 1, 2, 3, 4, 5, and 12.

##### *Pharmacodynamic (PD) Population*

Subjects who received at least one dose of study treatment (ARO-HBV, JNJ-6379, or placebo) and had PD assessment from baseline and  $\geq 1$  assessment from post-baseline will be included in the PD population. Subjects will be summarized according to the treatment they received.

Subjects with protocol violations will be assessed on a subject-by-subject basis for inclusion in the PD Population. The determination of study populations will be made, prior to unblinding the PD data, at the blinded data review meeting before the final analyses. The PD population will be used for the summaries of all immunologic endpoints, virology endpoints, cytokines and complement.

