### **2.2.2 Secondary objective(s)**

- To evaluate the single-dose pharmacokinetics of ARO-HBV in healthy volunteers
- To determine the reduction from Day 1 pre-dose baseline to post-dose nadir of HBsAg in response to ARO-HBV in CHB patients as a measure of activity

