### CHB Cohorts

All CHB patients in each of the 13 CHB cohorts will receive ARO-HBV (alone or in combination with JNJ-6379) and daily NUC, and no randomization is applied.

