## 11. VIROLOGY

Virology endpoints are only collected for CHB cohorts across the study period according to the protocol schedule of assessment. The analysis population for virology data is PD.

Virology endpoints will be analyzed separately for the main study (up to Day 113 EOS) and for the overall study duration, including the follow-up period, for the subset of patients that consented to participate in the follow-up. Endpoints will be derived separately for each analysis taking into consideration all the applicable data for the specific period.

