### **17.2 Interim Analyses**

An interim analysis of the safety and PD data was planned and performed in May 2019 (data cut-off 27Mar2019). This interim analysis was conducted to assist with the planning of future studies and Health Authority interactions and did not impact the conduct of this study. The Sponsor was unblinded to selected summary data only.

A second interim analysis based on all study data up to Day 113 for all cohorts, was completed in February 2020 (data cut-off 14Nov2019).

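### In the open-label CHB cohorts, patients with protocol violations can be dropped from the PD Population case by case, with no named grounds and with Day 113 results already analysed

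*SAP*

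**What the plan says.** **Population rule.** SAP Section 4 (Pharmacodynamic Population) admits anyone who was dosed and has a baseline and at least one post-baseline PD assessment. It then qualifies this: "Subjects with protocol violations will be assessed on a subject-by-subject basis for inclusion in the PD Population". On timing it says: "The determination of study populations will be made, prior to unblinding the PD data, at the blinded data review meeting before the final analyses". For the CHB cohorts the opening of Section 4 adds: "The same process will be applied to the CHB cohorts as well even if there is no blinding for these cohorts".

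**What depends on it.** SAP Section 11 states: "The analysis population for virology data is PD". That covers the secondary objective in SAP 2.2.2: "To determine the reduction from Day 1 pre-dose baseline to post-dose nadir of HBsAg in response to ARO-HBV in CHB patients".

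**Design of these cohorts.** They are open label and not randomised. SAP 2.5 says: "All CHB patients in each of the 13 CHB cohorts will receive ARO-HBV (alone or in combination with JNJ-6379) and daily NUC".

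**What has already been analysed.** SAP 17.2 reports an interim of safety and PD data in May 2019 (cut-off 27 March 2019). It also reports this, completed in February 2020: "A second interim analysis based on all study data up to Day 113 for all cohorts". The HBsAg summary tables and the individual-patient HBsAg plots are marked for the Day 113 interim (SAP Sections 19 and 21).

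**Analysis of all dosed patients.** Protocol 11.6 commits to a separate analysis of every CHB patient who received at least one dose. The closing part of SAP Section 11 makes this optional and possibly post hoc.

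**The concern.** A case-by-case exclusion rule is normally acceptable because those applying it cannot see how the exclusion would change the result. HBsAg is measured only in the CHB cohorts, so blinding never protects this endpoint. By the time of the final population decision, Day 113 HBsAg values had been tabulated and plotted by patient.

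No written criteria limit the discretion. SAP Section 6 says that medical monitors will assign each deviation a category and points to a list below. What follows is only a set of examples, such as missed or out-of-window visits, with no classes and no link to the PD Population. Many patients could therefore come up for review.

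Cohorts are small: 4 to 8 patients in 1b to 5b, at most 4 in 6 to 11, and 12 in Cohort 12 (SAP 2.4). One exclusion can visibly change a cohort's mean decline, its spread and its response rate. SAP 2.4 says the results will feed sample size calculations for later studies, and a larger mean with a smaller SD would push those sizes down.

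**Working it through.** **1. Cohort sizes.** Taking Cohorts 6 to 11 at their cap of 4:
- minimum 6×4 + 6×4 + 12 = 60
- maximum 6×8 + 6×4 + 12 = 84

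Both match SAP 2.4, so n = 4, 8 and 12 are the relevant cases.

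**2. Worst single exclusion, cohort mean.** Removing the smallest of n values raises the mean by (mean − minimum)/(n − 1). For normal data the expected rise, in SD units, is E[max of n]/(n − 1). In standard errors of the cohort mean it is that figure times √n.

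| n | E[max of n] | Shift (SD) | Shift (SE) |
|---|---|---|---|
| 4 | 1.029 | 1.029/3 = 0.343 | 0.69 |
| 8 | 1.424 | 1.424/7 = 0.203 | 0.58 |
| 12 | 1.629 | 1.629/11 = 0.148 | 0.51 |

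**3. Worst single exclusion, spread.** By simulation of normal samples, the cohort SD is multiplied by about 0.76 (n = 4), 0.85 (n = 8) and 0.88 (n = 12).

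**4. On the log10 scale.** The documents give no SD for HBsAg change, so a range is assumed.

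| Assumed SD (log10) | n = 4 | n = 8 | n = 12 |
|---|---|---|---|
| 0.3 | 0.10 | 0.06 | 0.04 |
| 0.5 | 0.17 | 0.10 | 0.07 |
| 1.0 | 0.34 | 0.20 | 0.15 |

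**5. Response rates.** Dropping one non-responder turns 1/4 = 25% (exact 95% CI 0.6 to 80.6%) into 1/3 = 33% (0.8 to 90.6%). In Cohort 12, 1/12 = 8.3% would become 1/11 = 9.1%.

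**6. Exclusion unrelated to outcome.** The expected shift in the mean is 0. The expected SD ratio is 0.96 (n = 4) or 0.99 (n = 8). The harm therefore comes entirely from any link between exclusion and result.

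**7. The other HBsAg filter.** SAP Section 11 leaves patients with a baseline below the quantitation limit out of post-dose summaries. Entry requires HBsAg of at least 5 IU/mL against a limit of 0.05 IU/mL, so this should remove almost no one. It is also fixed before treatment. The case-by-case clause is the route that matters for HBsAg.

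**The case against.** **The SAP is open about the lack of blinding.** A reader might infer that it claims a blind that does not exist. It does not: Section 4 concedes the point for the CHB cohorts. The PD Population also serves cytokines and complement in the placebo-controlled NHV cohorts, where a blinded review has meaning. This stands. The problem is unguarded discretion, not a false claim, and it does not extend to the NHV cohorts.

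**Not every cohort is known to have been analysed twice.** SAP 17.2 does not name the cohorts in the first interim. Cohort 12 came in with protocol Version 5.0, dated 4 January 2019. Even dosing on that date puts Day 113 at 26 April 2019, after the 27 March cut-off. Only the second interim is stated to cover all cohorts to Day 113, and that is enough for the point.

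**The shifts are worst cases.** They require the least favourable patient to have a violation and to be the one removed. A reader might take 0.34 SD as the expected bias, but the documents do not support that.

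**Consequences are limited.** HBsAg is secondary and descriptive, and SAP 2.4 disclaims hypothesis testing. The primary safety objective uses the Safety Population and is untouched.

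**There are partial safeguards.** Population counts are reported, deviations are reviewed before database lock and listed, and the February 2020 tables would let someone who holds them detect a later exclusion. But counts do not show whether exclusions tracked outcome. SAP Section 11 promises listings of all virology data, yet Section 20 assigns the HBsAg listing to the PD Population, so an excluded patient may not appear there.

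**Keeping violators has a price.** A patient who took a restricted immunomodulator could bias virology and not merely add noise. This stands, and is the reason for a sensitivity analysis.

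**Conclusion.** The point holds as a gap in the safeguard for the CHB cohorts. The SAP allows unspecified, patient-level exclusions from the population that carries HBsAg, in cohorts it acknowledges are unblinded, after all Day 113 data have been analysed. It also makes optional the protocol's analysis of all dosed patients, which would have shown the effect of any exclusion.

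The size is an upper bound for one exclusion: about 0.34 SD (n = 4), 0.20 SD (n = 8) or 0.15 SD (n = 12) in a cohort mean. This assumes normal data and removal of the least favourable patient. The log10 equivalents rest on an assumed SD. No type I error or power is at stake. The case for changing the text is that an objective rule already stands in the same section and is less open to bias.

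**What to change.** For the CHB cohorts only:

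1. Delete the case-by-case clause from the PD Population, together with the wording that places the decision before unblinding of the PD data.
2. Make the main virology analysis, by cohort, all dosed patients with a baseline and at least one post-baseline value. This restores as mandatory the intent of the all-dosed analysis in protocol 11.6. The baseline quantitation-limit rule can stay.
3. Present any removal of violators only as a sensitivity analysis. Name the qualifying deviations in SAP Section 6, where the categories are now undefined, and report exclusions with reasons by cohort.

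The NHV cohorts may keep the blinded-review wording.

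The cost is SAP text and one conditional set of tables, with no new data. The downside is that patients with deviations, including use of restricted medication, stay in the main analysis and may add noise or some bias. The sensitivity analysis would show how much.
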